3.2 Study Rationale

DAA therapy has made it possible to effectively and safely treat HCV before or after kidney transplant. However, most waitlisted end-stage renal disease patients are predicted to live longer with transplant than on dialysis;¹⁹⁻²¹ this benefit extends to HCV-infected patients. Approximately 500 kidneys from HCV-infected donors are discarded annually in the United States. Strategies to increase utilization of HCV-infected kidneys to shorten wait time for patients on dialysis are desperately needed.²² The purpose of this study is to determine if G/P treatment when initiated early after kidney transplant (e.g., as early as 3 days post-transplant) can prevent significant HCV viremia and prevent establishment of HCV infection in the liver and associated complications. G/P's registration program has demonstrated high efficacy with an overall SVR12 rate of 98% for the label-recommended regimen/duration, good safety and tolerability. These data suggest that G/P may achieve similar high SVR12 rates and safety results in HCV negative recipients of HCV viremic kidneys when G/P treatment is started early post-transplant.

3.3 Benefits and Risks

Potential benefits of early post-transplant treatment with G/P in the setting of high unmet need subjects on the kidney transplant wait list include:

1. Potential for high SVR rate in a population with long and/or additional waiting times on the kidney transplant list and substantial risk for health complications before a good-quality HCV-negative kidney becomes available for transplantation.
2. The approved dose of G/P e.g., 300mg/120mg (=3 tablets) once daily can be used in subjects with or without any level of renal impairment and for all HCV genotypes 1-6.
3. The safety profile and high efficacy (98% SVR12 with no virologic failure) of G/P in subjects with end-stage renal disease has been established.
4. G/P demonstrated good tolerability, safety and high efficacy in patients treated for chronic HCV infection post kidney transplantation.
5. The benefit of a short 8 week therapy and no Ribavirin (RBV) needed as part of the treatment regimen

6. The benefit of early treatment initiation of G/P after transplant of an HCV RNA-positive allograft greatly reduces the risks of sequelae of acute HCV infection.

The safety of G/P has been established in a diverse population of patients with and without compensated cirrhosis in Phase II and III clinical trials (Section 3.1.4). The most common AEs in greater than 10% of subjects include headache, and fatigue. Additional Safety data for G/P are detailed in the Mavyret USPI.¹⁰ In addition, subjects may experience inconvenience or discomfort related to the study visits or study procedures.

Risks associated with acute HCV infection,^{15,23} the treatment with G/P, including the risks of medication toxicity, virologic failure, and development of resistance-associated substitutions (Section 3.1.3), appear to be limited and manageable based upon the available data. A subject experiencing G/P treatment failure in this study will be offered retreatment with a regimen deemed suitable. Given the potential for high rates of SVR in this population with limited current treatment options, the risk-benefit assessment is favourable.

4.0 Study Objectives

4.1 Primary Objective

The primary objective of this study is to demonstrate the safety and efficacy (SVR12) of an 8-week treatment with G/P in HCV-negative recipients who received a study eligible HCV RNA-positive kidneys in Arm 1

4.2 Secondary Objectives

The secondary objectives are:

- 1) Among all subjects enrolled in the study, to describe time to kidney transplant and cumulative incidence of each type of transplant: a study-eligible HCV RNA-positive kidney (Arm 1), a study-eligible HCV RNA-negative/HCV antibody-positive kidney (Arm 2A), or a kidney transplant performed as part of standard of care treatment (Arm 2B).

2) To describe clinical outcomes while on the waitlist after consent (Serious Adverse events [SAEs], delisting from waitlist, death) between those who receive a study-eligible HCV RNA-positive kidney (Arm 1) and in subjects consented for this study who do not receive a study-eligible kidney transplant from an HCV RNA-positive donor (all Arm 2 subjects) overall and with breakdown by the 3 categories of Arm 2 as below:

A: subjects who receive a kidney from a study-eligible HCV RNA-negative/HCV Ab-positive donor

B: subjects who receive a standard of care kidney transplant

C: subjects who were not transplanted within 1 year of consent

Hereafter, these categories will be referred to as Arms 2A, 2B and 2C.

A “standard of care” transplant will be defined as any of the following kidney transplants: a deceased donor HCV RNA-positive kidney transplant that did not meet donor criteria for Arm 1 or HCV RNA-positive kidney transplant that place after last transplant allowed for Arm 1 but met criteria for Arm 1 inclusion (2B1); a deceased donor HCV RNA-negative/HCV Ab-positive kidney transplant that either did not meet donor criteria or took place > 6 months after the last Arm 1 transplant (2B2); a deceased donor HCV RNA-negative/HCV Ab-negative transplant at a MYTHIC clinical site (2B3); any living donor kidney transplant at a MYTHIC clinical site (2B4); or any kidney transplant at a different center than the 7 clinical sites (2B5).

In addition, to compare the total number of inpatient hospital days while on the waitlist and after study consent in those who did receive a study eligible HCV RNA-positive kidney (Arm 1) vs total inpatient hospital days in those who did not (Arm 2) overall and with breakdown by the 3 categories of Arm 2 (2A, 2B and 2C).

3) To describe clinical outcomes and data post-transplant (death, graft failure, acute allograft rejection, delayed graft function, estimated glomerular filtration rate [eGFR], proteinuria, ALT elevation > 5 times the upper limit of normal (ULN), SAEs)

between those who receive an HCV RNA-positive kidney (Arm1) and in subjects who receive an HCV RNA-negative/HCV Ab-positive kidney allograft (Arm 2A) or a standard of care kidney transplant (from Arm 2B1 – 2B4) combined and separately. For subjects of Arm 1 and Arm 2A who become HCV infected, we will collect additional clinical outcomes of sclerosing cholestatic hepatitis and extrahepatic manifestations of HCV. In addition, the clinical outcomes and data post-transplant will be compared between Arm 1 and Arm 2 where a) any study drug (G/P) related severe treatment emergent adverse events are included as a clinical outcome for Arm 1 and b) all events of treatment emergent Grade \geq 3 laboratory values and severe G/P-related treatment emergent adverse events are included as clinical outcomes for Arm 1.

- 4) To compare time to deceased donor kidney transplantation among all patients who enrolled in this MYTHIC trial to transplant candidates from the Organ Procurement and Transplantation Network (OPTN) database; MYTHIC participants will be matched 1:3 to OPTN patients on demographics and characteristics known to influence waiting time including waiting list priority, blood group, geographic region, and sensitization.

5.0 Investigational Plan

5.1 Overall Study Design, Rationale and Plan: Description

This is a Phase 4, open-label, multi-center, 2-arm study with the primary objective of evaluating the efficacy (SVR12) and safety of the fixed-dose combination tablets of glecaprevir/pibrentasvir (G/P) in HCV-negative subjects who receive a kidney transplant from an HCV RNA-positive deceased kidney donor. Among 90 subjects consented for trial participation, 30 subjects at up to 7 sites are planned to receive an HCV RNA-positive kidney and will be enrolled into a post-transplant treatment arm (Arm 1) receiving open-label G/P for 8 weeks post-transplant. The remaining consented patients who do not receive a study eligible kidney from an HCV RNA-positive donor will be followed in Arm 2 for the minimum duration of 1 year post-enrollment (Arm 2B and 2C), or 24 weeks post-transplant, whichever is longer (Arm 2A). These Arm 2 subjects include patients who do

not receive a kidney transplant (Arm 2C) or who receive a study eligible kidney from an HCV RNA-negative/HCV Ab-positive donor (Arm2A), or from a standard of care donor (Arm 2B). Follow-up for study participants who receive a kidney transplant at a non-study site (Arm 2B5) will be censored at transplantation.

For subjects of Arm 1 of the study, the first dose of G/P will be given as early as 3 days post-transplant. Patients must be out of the ICU, able to eat and drink, take oral medications, and G/P treatment can be safely initiated orally as judged by the site investigator.

Enrolled subjects will be activated in the United Network for Organ Sharing (UNOS) allocation system as eligible for kidney allograft offers from deceased donors that are HCV RNA-positive, HCV Ab-positive, or both.

Subjects who are transplanted with kidneys from HCV RNA-positive donors in Arm 1 will be followed for 1 year after the date of transplantation to evaluate SVR12, SVR24, safety, death, graft failure, acute allograft rejection, delayed graft function, ALT elevation >5 times the upper limit of normal, eGFR and proteinuria. Specifically, scheduled in-person visits for subjects who received organs from HCV RNA-positive donors in Arm 1 and receive G/P treatment will consist of day of transplant, Day 1 of G/P treatment, weeks 1, 2, 4, and 8 (planned end of treatment visit) after starting G/P. Additional scheduled visits will take place at Post Treatment Week 4, Post Treatment Week 12, Post Treatment Week 24 (e.g., post G/P treatment visits) to evaluate SVR4, SVR12 and SVR24 and 1 year post transplant. The post-transplant study visit schedule for MYTHIC has been designed such that these visits should take place on the same days as standard of care clinical visits. For subjects in Arm 1 study-objective pertinent data will be collected while awaiting a transplant (ie, SAEs, hospitalizations, delisting from waitlist, death), and post-transplant (ie, death, graft failure, acute allograft rejection, delayed graft function, eGFR, proteinuria, ALT elevation >5 times the upper limit of normal, and SAEs). Subjects who experience virologic failure in

Arm 1 will be evaluated for the emergence/persistence of DAA-resistant viral variants, and suitable retreatment will be offered.

Study visits in Arm 2A will take place at weeks 1, 4, 8, 12, and 24 weeks after transplantation. Safety, graft survival, mortality, allograft rejection, and results of HCV RNA testing will be captured for a period of 24 weeks post-transplant. Study-objective pertinent data will be collected while awaiting a transplant (i.e., SAEs, delisting from waitlist, death), and post-transplant (i.e., death, graft failure, acute allograft rejection, delayed graft function, eGFR, proteinuria, ALT elevation >5 times the upper limit of normal, and SAEs). For subjects of Arm 1 and Arm 2A who become HCV infected, we will collect additional clinical outcomes of sclerosing cholestatic hepatitis and extrahepatic manifestations of HCV.

If any recipients of a study-eligible HCV RNA-negative/HCV antibody-positive kidney develops HCV infection within 24 weeks after transplantation, that recipient will be offered treatment with G/P for 8 weeks. G/P treatment will be administered and subject will be followed as per local transplant center standard of care not reimbursed by the study but G/P will be supplied by the study. Limited data of this “reactive” G/P treatment and HCV outcome will be collected from these subjects. The following data will be obtained: plasma HCV RNA prior to HCV treatment initiation with G/P, SAEs that occurred during the G/P treatment period, any early discontinuation of G/P treatment, HCV RNA results at post treatment week 12, , and reasons for not achieving SVR12, as applicable. In the case of active HCV viremia, a sample of plasma and PBMCs will be sent to MGH as early as possible after viremia is detected.

Other subjects in Arm 2 who remain on the transplant waiting list, or receive a standard of care kidney transplant will be followed as per transplant center standard of care for at least 12 months post enrollment with study-objective pertinent collection of data while awaiting a transplant (e.g., SAEs, delisting from waitlist, death), and post-transplant events as

applicable (death, graft failure, acute allograft rejection, delayed graft function, eGFR, proteinuria, ALT elevation >5 times the upper limit of normal, and SAEs). However, for Arm 2B5 recipients, no further data will be collected after transplantation.

During the first 6 months after the trial commences, each study site will be assured of the ability to perform at least one kidney transplantation from an HCV RNA-positive donor and G/P therapy provided through the trial. The period of “the first 6 months after the trial commences” will start on the date that the first clinical site has institutional review board approval to start enrolling patients into the trial until 183 days later. The other kidney transplants from HCV RNA-positive donors will take place competitively, such that any site may perform kidney transplants up to a maximum of 10 transplants from HCV-RNA-positive donors with recipients receiving study drug and being analyzed in Arm 1.

Treatment Period for recipients of HCV RNA-positive kidneys in Arm 1:

[figure not shown]
Eligible subjects will initiate G/P 300 mg/120 mg QD for 8 weeks early after kidney transplantation. Day 3 post-transplant is targeted for the start of G/P treatment for HCV RNA-positive kidney recipients, with the conditions met that the subject should be out of the ICU, able to eat and drink and take medications orally, and in the judgement of the investigator, starting oral G/P treatment is safe for the subject.

A delay in commencing G/P after day 3 should only take place because the responsible site investigator and/or responsible clinicians believe that G/P cannot be safely administered or because of a high probability that G/P will subsequently need to be discontinued or held for prolonged period because the patient is likely to experience clinical deterioration. In the case of any patient who has not started G/P by day 3 after transplantation, the site investigator will discuss that case with the Principal Investigator [name], or delegate, and develop and document a plan to start G/P at a later time.

Post Treatment (PT) Period for recipients of HCV RNA-positive kidneys in Arm 1:

Subjects who complete or prematurely discontinue G/P treatment will be followed for 24 weeks after their last dose of study drug to evaluate efficacy and to monitor HCV RNA and the emergence and persistence of viral substitutions in the NS3 and NS5A, and subjects will be followed up at 1 year post the date of kidney transplant to assess graft function and survival and anti-HCV antibody serology.

Figure 1A: Overall Study Schematic

[figure not shown]
Treatment and PT Period for Study Arm 2A recipients of HCV RNA-negative/HCV antibody-positive kidneys:

Eligible subjects will be followed for 24 weeks after transplantation or 12 months after enrollment, whichever is longer, with surveillance for HCV infection using HCV RNA testing on week 1, week 4 (usual care), and week 24 (Figure 1B) after transplantation. A maximum number of up to n=20 subjects who are enrolled into the study can accept a study-eligible kidney from an HCV RNA-negative/HCV antibody-positive donor and be assigned to Arm 2A and will be followed in the study for 24 weeks post-transplant. The last study-eligible kidney transplant from an HCV RNA-negative/HCV antibody-positive donor in Arm 2A must occur no later than 24 weeks after the date of the 30th kidney transplant from an HCV RNA-positive donor in Arm 1 (see also section 5.1.5).

Any subject in Arm 2A who develops HCV infection by 24 weeks after transplantation will be offered open-label G/P 300 mg/120 mg QD for 8 weeks. G/P will be provided by AbbVie, and while all patients will receive an 8-week course, the patient treatment visit schedule

and follow-up will be guided by the transplant center standard of care and AASLD/IDSA Guidelines for HCV treatment²⁶, and as described in section 5.1.1, 5.1.2 and Table 6. Outcome data, including SAEs, treatment emergent Grade 3 or greater laboratory abnormalities, sclerosing cholestatic hepatitis and extra-hepatic manifestations, and post-treatment week-12 HCV RNA will be collected from the subject medical record and entered into the study eCRFs. For kidneys from HCV RNA-negative/HCV Ab-positive donors in Arm 2A, the inclusion/exclusion criteria for donors are identical to donor inclusion/exclusion criteria as outlined in section 5.2.1 and 5.2.2, except that donor must be HCV RNA-negative.

Figure 1B: Schematic for patients undergoing transplantation with HCV RNA-negative/HCV antibody-positive kidney in Arm 2A

Observation period for other Study Arm 2 subjects

Enrolled Arm 2 subjects who were not transplanted will be followed for 1 year post enrollment and Arm 2 subjects who received an standard of care kidney (Arm 2B) will be

followed for a minimum of 1 year post-enrollment, or 24 weeks post transplantation whichever is longer, unless they are transplanted at a non-study site (Arm 2B5), in which case no further data will be collected after transplant.

5.1.1 Standard of Care Assessments for all patients – (patient managed clinically and billed per standard medical practice)

1. Subject assessment for kidney transplant candidacy, kidney transplantation, and follow-up care after transplant; prior HCV treatment history; medical history; co-morbid conditions; for-cause kidney biopsy or for cause liver biopsy, due to new or worsening symptoms of pre-transplant kidney or liver disease; or post-transplant delayed or decreasing kidney graft function with suspicion for FSGS, graft rejection, or suspicion for post-transplant fibrosing cholestatic hepatitis, or other new liver disease.
2. Donor kidney assessment and organ procurement, and including HCV RNA
3. Assessment of recipient and donor-organ match
4. G/P treatment regimen monitoring that takes place as part of SOC visits
5. Clinical factors (physical examinations, vital signs)
6. Adverse events and related safety management
7. Concomitant medications
8. Assessments during waitlist period
9. Clinical Chemistry and Hematology labs
10. Pregnancy tests post-transplant, except as noted below for research purposes
11. Drug level monitoring of tacrolimus or other immunosuppressants post-transplant

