5.1.9 Additional Visits

Additional visits will only be necessary in the case of G/P treatment failure of subjects who received an HCV RNA-positive kidney. After treatment failure has been confirmed, a suitable retreatment regimen will be provided by the MYTHIC study. The retreatment regimen will be chosen at the discretion of the overall PI, [name] with input from the site investigator. The retreatment of study subjects, however, will be followed by the site investigator and as per local center standard of care. The following information of standard-of care visits for retreatment of a subject who failed G/P in this study will be obtained: Any SAE and relatedness of SAE to retreatment regimen from the 1st dose of retreatment regimen to 30 days post last dose of retreatment regimen; Any retreatment regimen emergent laboratory abnormality \geq Grade 3 until 2 days post last dose of retreatment regimen; any early discontinuation of retreatment regimen, reason for not achieving SVR12; HCV plasma RNA before start of re-treatment regimen and 12 weeks after end of re-treatment.

5.1.10 Schedule of events for patients who receive no transplant or standard of care kidney transplant

Enrolled subjects who undergo a standard of care kidney transplant or who remain on the transplant waiting list will have limited study visits and procedures. These subjects will be followed for a minimum of 1 year post enrollment if they did not receive a transplant during that time. Subjects who received a standard of care kidney transplant will be

followed for 24 weeks post transplant or a minimum of 1 year post enrollment, whichever is longer.

After enrollment and while on the waiting list, there will be telephone contacts with study subjects every two months to ascertain interim events of importance to protocol-data collection, including non-SAE hospitalizations, SAEs, change in wait list status. For those who have a standard of care kidney transplant, death, graft failure, acute allograft rejection, delayed graft function ALT elevation > 5x ULN, eGFR, proteinuria (as available) and SAEs will be obtained from the subject's medical record. eGFR will be measured at each standard of care clinic visit, with particular focus on the 6-month visit. These data will be entered into study eCRFs.

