6.1.4 Adverse Event Reporting

For this study, the AE reporting period will be divided based on the three phases of the study.

Pre-Treatment Phase

Screening phase: When all screening tests have been done, we will assess for any AEs related to the screening tests at the time of communication with the subject about whether he/she is official eligible or ineligible for the study.

Pre-existing Condition: A pre-existing condition is one that is present at the start of the study. A pre-existing condition should be recorded as an AE if the frequency, intensity, or the character of the condition worsens during the study period.

Waitlist phase: We will only capture AEs that are pertinent to the study. Specifically, the following will be captured:

1. Patient death,
2. Patient develops a condition that would exclude that subject from the study,
3. Patient is de-listed (taken off the kidney transplant waitlist)
4. Patient is made inactive on the transplant waitlist
5. Serious Adverse events and non-SAE hospitalizations; these will be categorized as “pre-transplant” (vs. “post-transplant”) and “pre-study drug” (vs. “post-study drug”)

In order to ascertain these events, we will review the patient’s medical history by phone every 2 months and in person every 6 months that they are on the wait list.

Treatment Phase in Arm 1

Immediate Post-transplant phase:

From the date of transplant with a HCV RNA-positive kidney to 1 day before first administration of the study drug, we will collect SAEs and clinical outcomes and data, including death, graft failure, acute allograft rejection, delayed graft function, eGFR, ALT elevation > 5 x ULN, SAEs.

HCV Treatment Phase

The following additional data will be collected from Day 1 of HCV treatment to 30 days following last dose of HCV treatment:

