All adverse events will be collected and clinical outcomes, including death, graft failure, acute allograft rejection, delayed graft function, ALT elevation > 5 x ULN, SAEs, sclerosing cholestatic hepatitis and extrahepatic manifestations of HCV, and data of eGFR and proteinuria. An assessment for causality to transplant, HCV infection, or study drug G/P will be made. Grade 3 or greater treatment-emergent laboratory abnormalities from the first dose of G/P through 2 days post dosing will also be collected and summarized. Events of sclerosing cholestatic hepatitis and extrahepatic manifestations of HCV infection will only be collected in ARM 1 subjects and subset of ARM 2A subjects who develop HCV viremia.

Post-Treatment Phase in Arm 1

Post HCV treatment Phase: From 30 days post last dose of HCV treatment to 1 year post kidney transplant (last study visit), the following outcomes and other data will be collected: death, graft failure, acute allograft rejection, delayed graft function, ALT elevation > 5 x ULN, SAEs, sclerosing cholestatic hepatitis and extrahepatic manifestations of HCV. eGFR and proteinuria will be collected at specific visits. All SAEs will be assessed at every clinic visit when the subject is seen by a member of the study team.

All unresolved AEs considered possibly, probably, or definitely related to the study drug or to HCV infection should be followed by the investigator until the events are resolved, the subject is lost to follow-up, or the AE is otherwise explained.

The investigator will notify the IRB of any death or SAE occurring at any time after a subject has discontinued or terminated study participation that may reasonably be related to this study. The IRB will also be notified if the investigator should become aware of the development of cancer or of a congenital anomaly in a subsequently conceived offspring of a subject that has participated in this study.

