Clinical outcomes post-transplant will include death, graft failure, acute allograft rejection, delayed graft function, ALT elevation > 5 times the upper limit of normal, and SAEs. In addition, HCV-infection related events of fibrosing cholestatic hepatitis and extrahepatic manifestations of HCV infection collected for Arm 1 subjects and only for Arm 2A subjects who develop HCV viremia will also count as clinical outcomes. The number and percentage of subjects with each and any clinical outcomes will be summarized for those who receive an HCV RNA-positive kidney (Arm 1) versus Arm 2 subjects combined and broken down (2A and 2B) as applicable. The difference in the overall percentage of subjects with clinical outcomes post-transplant in Arm 1 vs Arm 2A + 2B will be assessed by logistic regression with Arm as a factor and including appropriate covariates to adjust for possible differences between Arms including waiting list priority, blood group,

geographic region and sensitization, as appropriate given sample size and other statistical considerations. In addition, to include any clinical outcomes due to being treated with G/P, another summary of clinical outcomes post-transplant will include any study drug (G/P) related severe treatment emergent adverse events for Arm 1 subjects, and another will include events of treatment emergent Grade ≥ 3 laboratory values and related severe treatment emergent adverse events as clinical outcomes for Arm 1 subjects.

Analyses of the eGFR outcome will be calculated eGFR using the 4-variable MDRD equation. Mean (SD) eGFR will be summarized at appropriate visits and compared between Arms. Specifically, mean eGFR at 24 weeks/6-months post-transplant and 1 year post transplant will be compared between Arm 1 transplant recipients and the combined group of Arm 2A and 2B transplant recipients (2B1-2B4). As a secondary approach, mean eGFR at 24 weeks/6-months post-transplant will be compared between Arm 1 recipients and Arm 2A and 2B kidney recipients limited to those 2A and 2B recipients who did not develop HCV infection.

We will also compare estimated proteinuria between Arms 1 and 2A, including a count of individuals with >1000 mg/day estimated proteinuria. Proteinuria will be estimated using spot protein:Cr ratio.

An exploratory analysis will summarize the number and percentage of subjects with clinical outcomes post kidney transplant for the subgroups of Arm 2B.

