13	Arm 1	Acute allograft rejection	AAR: Binary (0/1) response. Compute OBS/EXP, where OBS=observed number of AARs for Arm 1 and EXP= expected cunt based on logistic regression model fitted to HCV-negative UNOS patients from large academic centers
14	Arm 1	ALT elevation	Binary (0/1), with '1' corresponding to peak ALT > 5 x ULN, where ULN=upper limit of 'normal'.
15	All, by arm	Serious Adverse Event	SAE: recurrent event Arm treated as a time-dependent factor Proportional rates model, robust SEs to account for within-patient clustering
16	Arm 1, 2AB	eGFR	Repeated continuous response Linear mixed model, to account for clustering by patient
17	Arm 1, 2AB	Proteinuria	Binary response; logistic regression
18	Arm 1, 2AB	BK virus	Binary response; logistic regression

Notes:

a) Each of the above-listed analyses will be accompanied by appropriate summary statistics (e.g., mean, median, IQR, etc).

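### After a standard-of-care transplant (Arms 2B1–2B4) SAEs are taken from the medical record with no scheduled contact, while Arms 1 and 2A are assessed at visits, so the between-arm SAE comparison leans against Arm 1 by an unknown, possibly small, amount

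*Protocol*

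**What the plan says.** **Arms 2B1–2B4.** Protocol 5.1 gives the follow-up rule for this group: "receive a standard of care kidney transplant will be followed as per transplant center standard of care for at least 12 months post enrollment". The same sentence goes on to include SAEs among the post-transplant data to be collected. Section 5.1.10 gives the method. It states "After enrollment and while on the waiting list, there will be telephone contacts with study subjects every two months to ascertain interim events". For those who then have a standard-of-care transplant, its list of outcomes ends "as available) and SAEs will be obtained from" the subject's medical record. Section 6.1.4 sets the same limit on calls: "medical history by phone every 2 months and in person every 6 months that they are on the wait list". No call or visit to ask about SAEs is scheduled for 2B after transplant.

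**Arm 1.** Table 5 ticks adverse-event assessment at all 12 contacts, V1 to V12. For the period after treatment, section 6.1.4 adds "All SAEs will be assessed at every clinic visit when the subject is seen by a member of the study team".

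**Arm 2A.** Section 5.1.7 has adverse events and clinical outcomes assessed at Visits 2 to 5, and at Visit 6 where that visit is needed.

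**Comparison.** The post-transplant outcomes in Protocol 8.1.4 include "delayed graft function, ALT elevation > 5 times the upper limit of normal, and SAEs". The overall percentage of subjects with an outcome is compared between Arm 1 and 2A + 2B by logistic regression. SAP Part 15 fits a proportional rates model to recurrent SAEs in all patients, with "Arm treated as a time-dependent factor".

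**The concern.** Under section 6.1.1.2 a hospital admission is an SAE, apart from listed exceptions. Section 9.4.1 expects about 40% of recipients to be readmitted within 30 days, so SAEs will be common and may dominate the post-transplant outcome.

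An event that never reaches the transplant center's record can still be found in Arm 1 or 2A by asking the patient. In 2B no scheduled step would find it. Admission to another hospital is plausible: section 5.1.3 anticipates candidates who travel a long distance to the site. In Part 15 the change of method coincides with the change of arm, because a 2B recipient's calls stop at the transplant that moves the subject out of waitlist time.

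At stake is the comparative safety statement about HCV RNA-positive kidneys. With identical true risk, unequal capture would make Arm 1 look worse. The covariates planned in 8.1.4 (waiting list priority, blood group, region, sensitization) do not address how events are found, and neither document names the difference as a limitation.

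**Working it through.** The documents give no SAE rate, power or target difference for this comparison, so there is no figure of the plan's own to reproduce.

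**Scheduled SAE contacts after transplant**
- Arm 1: 12 by Table 5, or 11 if V2 and V3 are combined as section 5.1.5.1 allows. Without the peri-transplant V1, these become 11 and 10.
- Arm 2A: four (Visits 2–5), or five with Visit 6. This count leaves out the peri-transplant visit.
- Arms 2B1–2B4: 0.

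**Effect on the Part 15 rate ratio.** Let s be the share of SAEs that record-only capture finds, relative to Arm 1, and w the share of comparator person-time in 2A, where capture is taken as equal to Arm 1. Neither value is in the documents; I take s = 0.95 to 0.80 and w = 0 or 0.5. With equal true rates:

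observed rate ratio, Arm 1 : comparator = 1 / (w + (1 − w)s)

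| SAEs missed in 2B | Comparator all 2B (w = 0) | Half the person-time 2A (w = 0.5) |
|---|---|---|
| 5% | 1/0.95 = 1.05 | 1/0.975 = 1.03 |
| 10% | 1/0.90 = 1.11 | 1/0.95 = 1.05 |
| 20% | 1/0.80 = 1.25 | 1/0.90 = 1.11 |

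**Effect on the 8.1.4 outcome.** Assume a Poisson mean of 0.8 SAEs per person, so P(at least one) = 1 − exp(−0.8) = 55.1%. With 20% missed, 2B shows 1 − exp(−0.64) = 47.3%. The odds ratio for SAEs alone is (0.551/0.449)/(0.473/0.527) = 1.37; with 5% missed it is 1.08.

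Section 8.1.4 tests any outcome, however, and a missed SAE changes nothing for a subject who already counts through another component. If 40% have an independent non-SAE component (assumed), the proportions with 20% missed are 1 − 0.6 × 0.449 = 73.0% and 1 − 0.6 × 0.527 = 68.4%. The odds ratio is then 1.25; with 5% missed it is 1.06. Visited 2A recipients in the comparator lower these further.

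**Precision.** Section 8.2 expects at least 40 transplants, with 30 planned for Arm 1; I take 10–30 comparators. At 55% in each group, the standard error of the log odds ratio is √[1/(30 × 0.2475) + 1/(n × 0.2475)]. This is 0.73 for n = 10 and 0.52 for n = 30. The 95% interval multiplies and divides the odds ratio by exp(1.96 × SE), about 4.2 and 2.8.

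**Calls needed to close the gap.** At one call per 365.25/6 = 60.9 days, 24 weeks gives 168/60.9 = 2.8 (2 complete intervals) and 52 weeks gives 364/60.9 = 6.0 (5–6 calls).

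**The case against.** Several counter-arguments carry weight.

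- **SAE duties are not specific to an arm.** Section 6.1 has the investigator monitor every subject, section 6.1.1.2 applies SAE reporting to all events after consent, and section 5.1.1 lists adverse events among standard-of-care assessments. All true, but none schedules a contact with the 2B patient. The site query about unreported SAEs starts from submitted records, so it cannot recover an event absent from them.
- **The contrast is not visits against records.** Arm 1 data are also abstracted from clinic and telephone notes (5.1.5), and Arm 1 visits are planned to fall on standard-of-care days (5.1). Most Arm 1 contacts fall between transplant and treatment week 8; four follow. This stands and narrows the gap. Arm 1 still has questioning in addition to records.
- **The stakes are limited.** Secondary objective 3 is mainly descriptive, section 8.2 calls the data preliminary, and the SAP table does not list the composite logistic test. This also stands.

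A reader might infer that 2B recipients have no study contact at all after transplant, or that calls are withdrawn from them alone. The text does not say so: section 5.1.10 speaks of limited study visits, and the two-monthly calls are a waitlist procedure in every arm. In Arms 1 and 2A scheduled visits replace them; in 2B nothing scheduled does. A reader might also infer that outside admissions are known to be missed, or that 1.37 is the distortion in the 8.1.4 test. The documents contain no evidence on missed events, and 1.37 concerns SAEs alone under assumed inputs.

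**Conclusion.** The point holds as a matter of design. Followed as written, the plan finds SAEs in 2B1–2B4 by a weaker method than in Arms 1 and 2A, then compares them. If any SAE is missing from site records, the error leans against HCV RNA-positive kidneys. It is clearest for Arm 1 against 2B and diluted where 2A is pooled in.

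The size is not derivable. Under the assumed 5–20% missed, the spurious Part 15 rate ratio is 1.05–1.25, or about 1.03–1.11 with half the comparator person-time in 2A. The effect on the any-outcome composite is smaller than on SAEs alone. Either may be small beside the sampling error. It is not established that the reported comparison will be materially wrong. The change is still worth making because it is specific and cheap and because neither planned analysis corrects for unequal capture.

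**What to change.** In Protocol 5.1.10, continue the existing two-monthly telephone contact after transplant for 2B1–2B4 recipients until the end of their follow-up, with the same SAE questions as in Arm 1. In the 8.1.4 and SAP Part 15 analyses, state the remaining difference in contact frequency as a limitation. If follow-up has already ended, only the limitation statement can still be added.

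The cost is about 2 short calls per 2B recipient over 24 weeks, or 5–6 over a year, by staff who already make such calls on the waiting list.

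Restricting the comparison to SAEs identifiable from the site record is not a useful substitute. Section 6.1.1.2 requires supporting records for every SAE report, so an Arm 1 event first elicited at a visit would usually be documented as well, and the restriction would separate little.
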